3.1. Study Design

This study will evaluate the effect of I-ACT with Check Yourself on adolescent-perceived quality of care (i.e., satisfaction and perception of PCP communication), motivation for health, and health risk behaviors using a stepped wedge study design. The study will take place in 6 participating PSPRN affiliated clinics, where the system of interventions (I-ACT with Check Yourself) will be rolled-out sequentially to the clinics, chosen in random order, over spaced time intervals (see Figure 1). We refer to pre-implementation of I-ACT with Check Yourself, as the control period and post-implementation as the intervention (i.e., case) period.

Figure 1: Stepped Wedge Study Design and Timeline

We anticipate that approximately 30% of youth approached will participate in the study. Thus, we will invite approximately 1000 adolescent/caregiver dyads to participate in the study, in order to yield 300 adolescent/caregiver dyad participants in our total sample. Upon enrollment, caregiver participants will be asked to complete a brief (10-minute) web-based questionnaire about their education/occupation, their adolescent's health history, and an open-ended question about what they would like to get from PCPs for themselves and their adolescent. Adolescents who enroll in the study will receive either electronic health screening alone (i.e., control group) if

their clinic appointment occurs in the pre-I-ACT implementation period or Check Yourself (i.e., intervention group) if their clinic appointment occurs in the post-implementation period.

At baseline (T1), adolescents will be asked to complete a web-based screening survey that includes questions about guideline-recommended health risk behavior screening areas, including substance use, nutrition, physical activity, sexual behavior, depressive symptoms, and safety. The screener questions themselves are current standard of care. Adolescents will also be asked to report their age, gender, race/ethnicity, interest in discussing health risks with the PCP, and self-efficacy.

Adolescents in the control group will complete the web-based screening survey for research purposes, but neither they nor their PCP will receive feedback about their health behaviors. PCPs will screen and counsel the patient as they would normally do under usual care conditions, consistent with the current standard of care.

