During the intervention period, participating PCPs will receive adolescent-centered communication training, based on the tenets of motivational interviewing, to reinforce healthy behavior choices and to engage youth and parents to reduce risk behaviors as appropriate. PCPs will also receive three feedback reports (baseline, 2 months and 4 months) on adolescent-reported receipt of counseling on each of the target behaviors and adolescent-reported visit satisfaction and follow-up care. PCPs will not be asked to complete any study questionnaires; all of the outcome data will be gathered directly from adolescents and caregivers. Outcome data for the three feedback reports will be given to providers in aggregate form and will be void of individual identifiers.

Adolescents in the intervention group will receive full personalized motivational feedback following completion of the screening survey, both with web-based delivery. Their PCPs will receive a summary report which will include specific information on the adolescent's responses that will allow them to reinforce healthy behavior choices and implement further brief, in-person interventions for moderate to high risk adolescents. The personalized feedback to the participant and provider is consistent with current standard of care. However, the electronic method of delivery is unique to this project.

In order to administer follow-up surveys, we will ask adolescents to provide an email address, cell phone number, or phone number. One day (T2) following their PCP appointment, adolescent participants will be asked via email, text message or phone to complete a survey about their motivation for health, perception of PCP communication, and experiences. Both adolescents and their caregivers will be asked about their satisfaction with treatment during the appointment with their PCP. In addition, caregivers will be asked open-ended questions to assess the provider's delivery of caregiver education regarding strategies to reduce health risks for their child during the visit.

Three (T3), six (T4) and twelve (T5) months following their PCP appointment, adolescent participants will be asked via email, text message or phone to complete all assessments

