intervention effects. Data set documentation will then be developed and distributed to the study team. Before carrying out analyses addressing each of the research questions, an analysis plan will be formally presented to the study team and Project Advisory Board so a wide range of expertise and experience is brought to bear on each work product of the team.

Some key features of the stepped wedge design require special consideration in the planned analyses. First, the design involves unidirectional cross-over from the control arm to the intervention arm for all PCPs. This has to be captured by an indicator specific to PCP and time point. Second, there are natural hierarchical structures in the data with PCPs nested within clinics, patients nested within PCPs, and repeated assessments made within patients for some outcomes, such as health risk behaviors. Because different patient samples will be surveyed at each time point, within patient correlation over time should not be strong. Still, clustering at the clinic and PCP-levels needs to be examined in all analyses. Third, secular time trends need to be carefully examined and separated from the intervention effect. Based on these considerations, we will focus on model-based approaches (linear or generalized linear mixed effects models) for the main analyses, in addition to standard hypothesis testing techniques.

Aim 1 will compare intermediary targets at all clinics before and after the intervention using an analytic approach that both accounts for design features, repeated assessments within adolescents, time trends in these target behaviors during study period and adjust for potential confounders. For this aim we will use patients as the units of analysis. We will consider outcomes at the level of the patient (adolescent reported motivation for health and provision of appropriate preventive counseling).

Our primary analysis will be based on a set of mixed effects regression models. As an illustration, let's consider the adolescent self-reported health motivation (readiness to change, as other adolescent reported outcomes can be modelled in a similar fashion. Specifically, we will consider the following regression model:

$$Y_{ijk} = \mu + \alpha X_{ijk} + \beta_k T_k + \gamma_k X_{ijk} * T_k + b_i + b_{ij} + \varphi \text{Covariates} + \varepsilon_{ijk},$$

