in which Y_{ijk} denotes the health motivation reported by j th patient within i th provider at k th time interval, X_{ijk} is a binary indicator of exposure to the intervention for the provider and the predictor of interest, T_k is a binary indicator of the k th assessment, b_i and b_{ij} are PCP and adolescent specific random effects that account for the within PCP and within adolescent correlations, and ε_{ijk} is the error term. Additional patient-level or PCP-level confounding variables can be adjusted in the model as well.

With this model, the fixed effects α captures the treatment effects on mean responses and time-by-intervention interaction coefficients γ_k 's captures the treatment effects across time. Fixed effects β_k 's aim to capture any temporal trend or learning effects. Using this approach, both within-adolescents and between adolescents information will be used to estimate the treatment effects. All coefficients will be tested using Wald test. Also note this

model framework is flexible enough that a patient can be enrolled at any time during the study and the model can accommodate different numbers of post-intervention assessments. For example, for an adolescent enrolled after his/her PCP has received intervention, all X_{ijk} 's would take value 1 for that subject.

We will apply linear mixed effects models for Gaussian outcome Y_{ijk} , and generalized linear mixed effects models for other types of outcomes (e.g., logistic model for binary outcome).

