For *Aim 2*, analyses will be based on patient survey responses to the 8-item satisfaction scale, patient perception of PCP communication, and the summary health risk variable, which will all be treated as continuous response variables. The summary health risk variable constructed from a count of dichotomized key risk behaviors (as shown in Table 2). First, satisfaction levels and risk behaviors will be summarized for each period (pre- and post-intervention) and will be compared using two sample t-tests. For the main analysis, we will apply mixed effects models similar to those proposed in Aim 1 to examine the intervention effect. For patient satisfaction, PCP satisfaction, adolescent's perception of PCP communication and health risk behaviors, the analysis will be cross-sectional comparisons at one day following the primary care visit. Let Y_{ij} denotes the satisfaction at one-day post visit of adolescent j within PCP i , let X_{ij} denote whether the PCP has received intervention at the time of visit, then the following mixed effects model can be applied

$$Y_{ij} = \mu + \alpha X_{ij} + b_i + \varphi \text{Covariates} + \varepsilon_{ij},$$

where b_i accounts for within-PCP correlations for adolescents seen by the same PCP. The fixed effect α captures the intervention effect on the patient satisfaction. Similar model can be applied to PCP outcomes and we can account for within-clinic correlations as well.

When examining the intervention effects on adolescents individual risky behaviors (alcohol use, marijuana use, unprotected sexual activity, depression, physical activity, healthy food consumption, seatbelt and helmet use) at baseline, 3, 6, and 12 months after the primary care visit, same modeling framework as outlined for Aim 1 can be applied.

3.3.3 Heterogeneity of Treatment Effects.

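### The models tie exposure to an undefined PCP receipt of the intervention rather than to the clinic's randomised crossover, with no rule for PCPs trained late or not at all

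*Combined protocol and SAP*

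**What the plan says.** Section 3.1 sets the allocation. The programme "will be rolled-out sequentially to the clinics, chosen in random order, over spaced time intervals". The two periods are named for the whole package: "We refer to pre-implementation of I-ACT with Check Yourself, as the control period and post-implementation as the intervention (i.e., case) period". An adolescent has screening alone if "their clinic appointment occurs in the pre-I-ACT implementation period or Check Yourself (i.e., intervention group) if their clinic appointment occurs in the post-implementation period". Group therefore depends on the appointment date and the clinic's implementation, and no other condition is stated.

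The same section says "During the intervention period, participating PCPs will receive adolescent-centered communication training". It gives no completion date relative to the clinic's step, and does not say whether all PCPs in a clinic are trained together.

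Section 3.3.2 defines exposure at provider level in three places:
- Of the crossover, which it describes as applying to all PCPs: "This has to be captured by an indicator specific to PCP and time point".
- In the Aim 1 model, X "is a binary indicator of exposure to the intervention for the provider and the predictor of interest". The worked example sets X to 1 throughout for an adolescent who enrols after the PCP has had the intervention.
- In the Aim 2 model, X is to "denote whether the PCP has received intervention at the time of visit".

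The plan does not say that X follows the clinic's randomised step or that analysis is by intention to treat. It has no rule for visits that precede a PCP's training or for a PCP who misses it.

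**The concern.** Only the clinics' rollout order is randomised. When an individual PCP completes training within a clinic is not. An exposure variable that depends on the PCP's own receipt is protected by the randomisation only as long as receipt and the clinic's step coincide, and the text does not guarantee that they do.

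Consider an adolescent seen after the step by a PCP who has not yet been trained. Under section 3.1 this adolescent gets web feedback, the PCP gets the summary report, and the adolescent belongs to the intervention group. Under the Aim 2 definition, with receipt read as training, X is 0. Two things follow. Some coded controls have had part of the intervention. And the visits that move to the control side belong to PCPs selected for training late or never, who may differ in communication and counselling, the very things that several outcomes measure.

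Because receipt is undefined, an analyst could also code the same visit 0 or 1, and could choose after seeing the data. The Aim 1 example refers to enrolment and the Aim 2 model to the visit, so the reference date is not uniform either.

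**Working it through.** The plan gives no effect size, SD, ICC or misclassification figure for this point, so there is nothing of its own to reproduce beyond the counts: 6 clinics × 5 PCPs = 30 PCPs, and 0.30 × 1000 = 300 adolescents (sections 2.1 and 3.1), hence 300/30 = 10 per PCP.

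**Step 1. Where the two rules differ.**

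| Visit | Group, section 3.1 | X, receipt = trained | X, receipt = clinic has rolled out |
|---|---|---|---|
| Before the step | control | 0 | 0 |
| After the step, PCP trained | intervention | 1 | 1 |
| After the step, PCP not trained | intervention | 0 | 1 |

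Only the third row matters, and only under one of two possible readings of receipt.

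**Step 2. How many adolescents would move.** Assume that half of the 300 visits (150) fall after the step, spread evenly over PCPs. Let f be the share of PCPs never trained. Then 150f adolescents move, and they make up f/(1+f) of the coded controls.
- 1 of 30 (f = 0.033): 5 adolescents, 3.2%.
- 3 of 30 (f = 0.10): 15 adolescents, 9.1%.
- 6 of 30 (f = 0.20): 30 adolescents, 16.7%.

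**Step 3. Selection bias when the true effect is zero.** Assume further that never-trained PCPs score 0.3 SD lower both before and after the step. They contribute no exposed visits and a share 2f/(1+f) of the coded controls. The raw difference is 0.3 × 2f/(1+f):
- f = 0.10: 0.3 × 30/165 = 0.055 SD.
- f = 0.20: 0.3 × 60/180 = 0.10 SD.

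The Aim 2 model has a PCP random intercept, which down-weights between-PCP information by k = (1 − ICC)/(1 + 9·ICC) with 10 visits per PCP. The expected generalised least squares coefficient is then 0.6·k·f/(1 + k·f), which returns the raw figures at k = 1.

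| ICC (assumed) | k | f = 0.10 | f = 0.20 |
|---|---|---|---|
| 0.01 | 0.908 | 0.050 SD | 0.092 SD |
| 0.05 | 0.655 | 0.037 SD | 0.070 SD |
| 0.10 | 0.474 | 0.027 SD | 0.052 SD |

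At ICC 0.05 the standard error is 0.115 SD for f = 0.10 and 0.118 SD for f = 0.20, so the bias is about one third (0.037/0.115) or 0.6 (0.070/0.118) of a standard error. Coding by the clinic's step gives zero bias in every cell.

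**Step 4. Dilution when training status is unrelated to outcome.** Set the full combined effect to 1 and let c be the part that Check Yourself produces without a trained PCP. PCP coding recovers 1 − c·f/(1+f); clinic coding recovers 1 − f(1 − c). At f = 0.20:

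| c | PCP coding | Clinic coding |
|---|---|---|
| 0 | 1.00 | 0.80 |
| 0.5 | 0.92 | 0.90 |
| 1 | 0.83 | 1.00 |

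Neither coding is always closer to the full effect. With f = 0, both give 1.00.

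**Step 5. The same check in a stepped layout.** Assume 6 clinics, 7 periods, 5 PCPs per clinic, one of whom is never trained, c = 1, and ICC 0.01 to 0.05. PCP coding recovers 0.84 to 0.88 without calendar-period terms and 0.66 to 0.68 with them. If that PCP is trained one period late instead, it recovers 0.95 and 0.88 to 0.89. Clinic coding recovers 1.00 throughout at c = 1; at c = 0 with one PCP per clinic never trained it recovers 0.80, against 1.00 for PCP coding.

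**The case against.** The best defence is that the plan sees no gap between the two rules. Section 3.3.2 has all PCPs crossing over, and section 3.1 has participating PCPs being trained. Eligibility requires an appointment with a participating provider, and providers consent after reviewing what the study expects of them. The periods are themselves named for the implementation of I-ACT with Check Yourself, so training may well open the period. The Aim 2 text also summarises outcomes by pre- and post-intervention period, which suggests that the authors treat PCP receipt and clinic period as one thing. Figure 1, the design timeline, is not visible in the text reviewed and may bear on the dates.

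This stands as far as it goes. A reader might infer that the plan codes adolescents of late or untrained PCPs as controls, or that it specifies an as-treated analysis. The documents do not support either reading: they describe no such PCP, and since the intervention is the training together with Check Yourself, a PCP receiving the summary reports could be read as exposed. It also stands that the two codings target different effects, and that PCP coding can be nearer the full combined effect when Check Yourself alone does little and training status is unrelated to outcome.

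What the defence does not supply is a rule. Saying that all PCPs cross over does not say that they do so on the clinic's date, and the main exposure definition should not depend on complete and punctual attendance.

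**Conclusion.** The point holds as a conditional one. Allocation is by the clinic's randomised implementation period; the models' exposure is by the PCP's receipt of something left undefined; and nothing ties the two together. If every PCP is trained at the step, the results are the same and nothing is lost. If some are trained later or never, and receipt is taken to mean training, the main comparison is no longer the randomised one.

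Its size cannot be drawn from the documents. The 0.03–0.05 SD (3 of 30 PCPs) and 0.05–0.09 SD (6 of 30) rest on assumed non-training, an assumed 0.3 SD deficit, an even split of visits and an ICC of 0.01 to 0.10. They are below the standard error of about 0.12 SD. The raw values of 0.055 and 0.10 SD should not be read as the expected bias, because they ignore the planned PCP random intercept. This is an inexpensive correction to make before analysis, not a defect that undermines the trial.

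**What to change.** In section 3.3.2, for the main analyses of both aims, define X = 1 when the index appointment falls on or after the clinic's randomised crossover date, for every participating PCP in that clinic and whatever that PCP's training date. State the crossover date for each clinic. Record each PCP's training completion date, define what counts as receipt for a PCP, and use PCP-receipt coding only as a sensitivity (as-treated) analysis.

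The cost is a few words in the model definitions and one recorded date per PCP. The estimand becomes the effect of rolling out the programme, which is diluted if some PCPs are untrained: for example 0.80 of the full effect if 1 in 5 are untrained and Check Yourself alone has no effect. For the repeated outcomes it also fixes X for each adolescent at the index visit. The Aim 1 text speaks of using information within adolescents, so it should say whether X was meant to change during follow-up when a PCP crosses over.

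### The Aim 2 one-day model has no calendar-period term, so α absorbs part of any drift over the stepped-wedge roll-out; the repair also needs a clinic intercept

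*Combined protocol and SAP*

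**What the plan says.** Section 3.1 describes a stepped wedge in 6 clinics, with the intervention "rolled-out sequentially to the clinics, chosen in random order, over spaced time intervals". Section 3.3.2 sets two requirements for the analysis: "secular time trends need to be carefully examined and separated from the intervention effect", and "clustering at the clinic and PCP-levels needs to be examined in all analyses".

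For the Aim 2 outcomes collected the day after the visit, the same section says that "the analysis will be cross-sectional comparisons at one day following the primary care visit". The equation printed for them contains an intercept, α times an indicator that the PCP was already trained at the time of the visit, a PCP random intercept, unspecified covariates and error. It has no time index and no clinic term. The text then says: "The fixed effect α captures the intervention effect on the patient satisfaction".

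Three other statements bear on the point:

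- The Aim 2 paragraph also says "we will apply mixed effects models similar to those proposed in Aim 1 to examine the intervention effect". In the Aim 1 model, "T_k is a binary indicator of the k th assessment".
- Clinic correlation appears in Aim 2 only as an option: "Similar model can be applied to PCP outcomes and we can account for within-clinic correlations as well".
- Section 3.3.3 prints a general model that does have time-interval effects and both clinic and PCP intercepts. It is illustrated with a PCP outcome, and similar models are promised for adolescent outcomes.

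**The concern.** In a stepped wedge, early visits are mostly control and late visits mostly intervention. Anything that moves the outcome over calendar time, such as season, clinic initiatives or a change in who enrols, is therefore correlated with exposure. Without period terms, α compares later visits with earlier ones as well as trained with untrained PCPs. The bias can run in either direction and does not shrink as more adolescents are enrolled.

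Table 1 lists satisfaction and perceived patient-centeredness among the main outcomes, and Section 3.1 names perceived quality of care first among the study's targets. A conclusion on these outcomes could be produced or hidden by drift alone.

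The missing clinic intercept is a second gap. Clinics are the randomised units. If they differ beyond what their PCPs explain, a PCP intercept alone understates the SE of α.

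**Working it through.** **Inputs from the protocol.** 6 clinics (Section 3.1); about 30 PCPs, 5 per clinic, and about 300 adolescents (Section 2.1); retention above 85% (Section 3.3.1), so a lower case of 0.85 × 300 = 255; Wald tests (stated for Aim 1). The plan prints no power, ICC or effect size, so there is no figure of its own to reproduce.

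**Assumed.** Figure 1 is not available, so 6, 3 and 2 steps were tried (1, 2 or 3 clinics per step). Outcome SD is 1. Clinic/PCP ICC pairs are 0/0, 0/0.03, 0.01/0.02, 0.02/0.03 and 0.05/0.05. Drift is linear, common to all clinics, from 0 in the first period to its full size D in the last. There is no true intervention effect.

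**Hand check, 6 steps, no clustering, equal enrolment.** In period t (0 to 6), t of the 6 clinics are exposed, giving 21 exposed and 21 control clinic-periods.

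- Mean period of exposed visits: Σt² / 21 = 91/21 = 4.33.
- Mean period of control visits: Σt(6−t) / 21 = 35/21 = 1.67.
- Share of drift in α: (4.33 − 1.67)/6 = 0.444.

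The same sum gives 0.556 with 3 steps and 0.667 with 2. The preliminary two-sample t-test in Aim 2 has exactly this bias.

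**With clustering.** By generalised least squares with known variances, the bias is the α element of (Z′V⁻¹Z)⁻¹Z′V⁻¹d, where Z is the model's design matrix, V its covariance and d the drift. A PCP intercept shifts weight towards before-after comparison within PCP, so the share rises slightly.

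| Model as printed, n = 300 | 6 steps | 3 steps | 2 steps |
|---|---|---|---|
| Share of D in α, equal enrolment | 44-51% | 56-61% | 67-71% |
| Share of D in α, five enrolment patterns | 31-61% | 38-72% | 40-87% |

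The five patterns over periods are equal, 1:3 rising, 3:1 falling, 3:1:3 U-shaped and 1:3:1 humped.

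**False positives.** The rate is Φ((−1.96·SEm + B)/SEt) + Φ((−1.96·SEm − B)/SEt), where B is the bias, SEm the model's SE and SEt the true SE. Example: 6 steps, ICC 0/0, D = 0.2. B = 0.444 × 0.2 = 0.089 and both SEs are √(1/150 + 1/150) = 0.115, which gives 12.0%. At ICC 0.05/0.05, B = 0.508 × 0.2 = 0.102, SEm = 0.117 and SEt = 0.125, which gives 15.7%.

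| 6 steps, model as printed | D = 0.1 SD | D = 0.2 SD | D = 0.3 SD |
|---|---|---|---|
| n = 300, equal enrolment | 7-9% | 12-16% | 21-27% |
| n = 300, five patterns | 6-9% | 8-20% | 13-37% |
| n = 255, equal enrolment | 7-9% | 11-14% | 19-24% |

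**Which part of the repair does what (6 steps, n = 300, equal enrolment).**

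- Clinic intercept without period terms: 44-54% of the drift remains, with 12-15% false positives at 0.2 SD.
- Period terms with the PCP intercept only: the bias is 0. At ICC 0.05/0.05, SEm is 0.167 against SEt 0.189, so the 5% test runs at 2Φ(−1.96 × 0.167/0.189) = 8.3% with no drift.
- Period terms with both intercepts: the bias is 0 and the rate is 5.0% with known variances.

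**Estimated variances.** A REML simulation (2,000 replicates, 6 steps, Wald z, three of the ICC pairs) gave 12.6-15.8% at 0.2 SD for the printed model. Period terms with the PCP intercept gave 6.2-9.6%, and period terms with both intercepts 5.8-6.3%. The Monte Carlo SE is about 0.5 points.

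**The case against.** The strongest reply is Section 3.3.3. Its model has interval effects and both intercepts, is introduced as the form of the primary analysis, and is to be carried over to adolescent outcomes. Its example is a counseling rate, which Table 1 collects only at the one-day survey, so the interval there most plausibly means a roll-out interval. On that reading the right model is already in the document, and the one-day equation is a loose illustration. Much of this stands: the plan knows the principle, and the defect is a conflict between its parts. But Section 3.3.3 is a general form in the heterogeneity section, and it does not say that its intervals are calendar time. The only equation written for the one-day outcomes drops both terms. The Aim 1 cross-reference does not settle it, because its time index is defined by assessment, and that is constant for an outcome measured once. The covariates slot and the later analysis plan would allow a period term, but do not commit to one.

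Section 1.1 speaks of exploring satisfaction and patient-centeredness, which argues for lower severity. Table 1 nevertheless places both among the main outcomes.

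The printed model also has the smaller root mean squared error until drift reaches about 0.23-0.26 SD (n = 300, equal enrolment). That is true, but it is a gain bought by assuming no trend, and it does not repair the test.

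**Conclusion.** The concern holds for the model as printed. Under any common drift, α in the one-day analysis is not the intervention effect alone. It takes roughly half the drift with 6 steps and more with fewer, because fewer steps leave less concurrent control. Clinics that have not yet crossed over prevent it from taking all of it.

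The direction of the argument rests only on the staggered design and the missing term. The sizes rest on assumed step count, ICCs, enrolment pattern and a linear drift, and nothing in the documents shows that drift of any given size will occur. The clinic intercept matters only if clinic-level variance is above zero, and its gain is small at low ICCs. Because the plan's own rules call for both adjustments, and because leaving two conflicting models allows a choice after results are seen, this should be corrected before outcome data are analysed.

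**What to change.** In the Aim 2 one-day model, index each visit by calendar period (roll-out step), add period fixed effects, and add a clinic random intercept alongside the PCP intercept. Make Section 3.3.3 agree with it.

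As clarification only, state in Aim 1 whether the time index is time since the visit or calendar period. If it is time since the visit, add separate calendar-period effects there too.

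The change adds one set of fixed effects and one variance component. Section 4.4 lists appointment dates among the data obtained from clinic scheduling, and the exposure indicator already needs visit timing; confirm that the date, or the period derived from it, reaches the analysis file.

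The real cost is precision. With n = 300 and equal enrolment, the SE of α rises from about 0.12 SD to 0.16-0.18 SD with 6 steps, 0.17-0.20 SD with 3 and 0.20-0.22 SD with 2. It reaches 0.31 SD with 2 steps and U-shaped enrolment. At an assumed 80% power and two-sided 5%, with 6 steps and ICC 0.02/0.03, the detectable difference moves from 2.80 × 0.117 = 0.33 SD to 2.80 × 0.174 = 0.49 SD, and should be restated. With only 6 clinics, a small-sample correction or a permutation test over the roll-out order would deal with the slight excess over 5% that remains with a plain Wald test.
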